2.13.1.5 Association of additional markers of disease progression on LCI at baseline

Number and percentage will be presented for the patients who took i.v. antipseudomonal therapy, and who were hospitalized due to exacerbations of lung disease.

Association between i.v. antipseudomonal therapy and LCI at baseline will be based on standard descriptive statistics (n, mean, standard deviation, median, minimum and maximum). Similarly, the association between hospitalization due to exacerbations of lung disease and LCI at baseline will be evaluated in the same way.

Analysis will be done for safety population based on observed data.

2.13.1.6 Patients with pathological LCI and pathological FEV1 at Baseline and at Week 4 and it's deviation from normal LCI and normal FEV1.

Number of patients with pathological LCI (i.e. LCI above 7.5) and normal LCI will be summarized by frequency and proportion. The summary of normal LCI and pathological LCI at baseline and at Week 4 will be presented by descriptive statistics (n, mean, standard deviation, median, minimum and maximum) for safety set.

Predicted FEV1 value will be calculated using below formula (Knudson)

Predicted FEV1 for Male subject aged <=24 yrs = 0.1168* Height (in Inches) + 0.0450*Age -4.808;

Predicted FEV1 for Male subject aged >24 yrs = 0.1321* Height (in Inches) - 0.0270*Age -4.203;

Predicted FEV1 for Female subject aged <=19yrs = 0.0686* Height (in Inches) + 0.0850*Age -2.703;

Predicted FEV1 for Female subject aged >19yrs = 0.0686* Height (in Inches) - 0.0210*Age -0.794;

Height in inches will be converted as: Height (in inches) = 0.39*height (in cm).

And percent predicted FEV1 will be calculated as: % predicted FEV1 = FEV1/Predicted FEV1*100.

Number of patients with pathological FEV1 (i.e. FEV1 below 75% predicted) and normal FEV1 will be summarized by frequency and proportion. Normal FEV1 and pathological FEV1 at baseline and at Week 4 will be summarized by descriptive statistics (n, mean, standard deviation, median, minimum and maximum) for safety set.

All by-subject exploratory efficacy data including air trapping (FRC_{ples} - FRC_{MBW}), S_{acin} (N2 slope acinar airways) and S_{cond} (N2 slope conductive airways) will be listed by age group, treatment dose form and visit(as applicable) along with date of assessment for safety set.

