1.2 Study objectives and endpoints

The objectives of study are as

Primary Objectives

The primary objective is to assess the change of LCI after 4 weeks following onset of study drug inhalation versus Baseline.

Secondary objectives

- Change of FEV1 % predicted after 4 weeks following onset of study drug inhalation versus Baseline.
- Change in CFU after 4 weeks following onset of study drug inhalation versus Baseline
- Change of LCI after 1 week following onset of study drug inhalation versus Baseline.
- Change of LCI, FEV1 % predicted and CFU between Week 4 (end of Study drug inhalation in the current treatment cycle) and Week 8 (prior to start of Study drug inhalation in the following treatment cycle).
- Correlation between the changes of LCI, FEV1 % predicted and CFU after 1 week, 4 weeks, and 8 weeks versus Baseline, respectively.

Exploratory objectives

- To explore the change in LCI between Baseline and Week 4 (week 0-4), and Week 4 and Week 8 (week 4-8), respectively, in patients using Tobramycin inhalation powder compared to patients using Tobramycin inhalation solution.
- To assess and compare S_{acin} (N2 slope acinar airways) and S_{cond} (N2 slope conductive airways) at baseline and at Visit 4 in patients using Tobramycin inhalation powder vs. patients using Tobramycin inhalation solution.
- To assess the changes in FEV1 % predicted and CFU from Baseline to Visit 3 (week 1) and to compare the change in FEV1 % predicted with the change in CFU and the change in LCI from baseline to Visit 3 (week 1) with the corresponding changes in FEV1 % predicted and CFU.
- To explore the change in air trapping (FRC_{ples} - FRC_{MBW}) after 1 week, 4 weeks, and 8 weeks versus Baseline, respectively.
- To explore the association of additional markers of disease progression (need for i.v. antipseudomonal therapy, hospitalization due to exacerbations of lung disease) on LCI at Baseline.
- To assess and compare the ratio of patients with pathological LCI and pathological FEV1 and their mean deviation from normal LCI and FEV1 at Baseline.
- To assess and compare the ratio of patients with pathological LCI and pathological FEV1 and their mean deviation from normal LCI and FEV1 at week 4.

2 Statistical methods

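### SAP 2.13.1.6 converts height at 0.39 inch per cm instead of 1/2.54, so % predicted FEV1 from its formula is too high for every patient and the count below 75% can only be too low

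*SAP*

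**What the plan says.** SAP 2.13.1.6 gives four prediction equations, by sex and age band, with height in inches and height coefficients to four decimals. For younger males the equation is "Predicted FEV1 for Male subject aged <=24 yrs = 0.1168* Height (in Inches) + 0.0450*Age -4.808"; for older males, "Predicted FEV1 for Male subject aged >24 yrs = 0.1321* Height (in Inches) - 0.0270*Age -4.203"; for younger females, "Predicted FEV1 for Female subject aged <=19yrs = 0.0686* Height (in Inches) + 0.0850*Age -2.703". Females over 19 have the same height coefficient, 0.0686, with an age coefficient of -0.0210 and a constant of -0.794. Height is collected in cm (SAP 2.3.3) and converted by this line: "Height in inches will be converted as: Height (in inches) = 0.39*height (in cm"). The section continues: "And percent predicted FEV1 will be calculated as: % predicted FEV1 = FEV1/Predicted FEV1*100". It then classifies patients: "Number of patients with pathological FEV1 (i.e. FEV1 below 75% predicted) and normal FEV1 will be summarized by frequency and proportion". This is planned at baseline and week 4.

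The output serves the exploratory objectives in SAP 1.2 that set pathological LCI beside "pathological FEV1 and their mean deviation from normal LCI and FEV1 at Baseline", and the same at week 4.

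SAP section 4 also moves the secondary FEV1 analyses from litres to % predicted, so that SAP 1.2 now reads "Change of FEV1 % predicted after 4 weeks following onset of study drug inhalation versus Baseline". Section 2.7.1.1, which covers that analysis, does not say how % predicted is obtained. The formula in 2.13.1.6 is the only one in the SAP.

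**The concern.** The exact factor is 1/2.54 = 0.3937; 0.39 agrees with it only to two decimals. The rounding error goes one way and is not diluted by the rest of the formula. It is amplified, because each equation adds a negative amount to the height term. The amplification is strongest where predicted FEV1 is small, that is, in young children and above all in young boys. Eligibility starts at age 6.

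At stake are the reported level of % predicted FEV1 and the number of patients called pathological on FEV1. A patient whose true value is a little below 75% is scored as normal. LCI has no such error, so the LCI-versus-FEV1 description can be biased only towards showing LCI as the more sensitive measure, which is the proposition the study is meant to examine.

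**Working it through.** **Inputs.** Conversion factor, equations, % predicted formula and 75% cut-off: SAP 2.13.1.6. Age range 6-50 years: protocol 5.1. Planned number 35, and FEV1 change of 5 with SD 9: protocol 10.7 and SAP section 3. Heights, age mix and baseline % predicted are not in the documents and are assumptions below.

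**Size of the conversion error.** 0.39 x 2.54 = 0.9906, so every height in inches is 0.94% too short. The SAP's own coefficients point to 2.54: 0.1168/2.54 = 0.0460, 0.1321/2.54 = 0.0520 and 0.0686/2.54 = 0.0270, all round values per cm. Multiplied by 0.39 they become 0.0456, 0.0515 and 0.0268.

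**Direction.** Write predicted FEV1 = b x k x H + c, where H is height in cm, k the conversion factor, b the height coefficient and c the age term plus the constant. All b are positive. c is negative throughout: at most 0.0450 x 24 - 4.808 = -3.728 for males up to 24, at most 0.0850 x 19 - 2.703 = -1.088 for females up to 19, and negative in both older bands, where age and constant both subtract. Lowering k by 0.94% therefore lowers predicted FEV1 by more than 0.94%, and % predicted rises for every patient. This holds at any height that gives a positive predicted value.

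**Size by patient.** Inflation = predicted(k = 1/2.54) / predicted(k = 0.39). The true value scored as exactly 75 is 75 divided by that ratio. For a boy of 10 at 138 cm:
- k = 0.39: 0.1168 x 53.82 + 0.450 - 4.808 = 1.928 L
- k = 1/2.54: 0.1168 x 54.33 + 0.450 - 4.808 = 1.988 L
- ratio 1.031; 75/1.031 = 72.7

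| Patient (height assumed) | Predicted, 0.39 (L) | Predicted, 1/2.54 (L) | Ratio | True % scored as 75 |
|---|---|---|---|---|
| Woman 25 y, 165 cm | 3.095 | 3.137 | 1.014 | 74.0 |
| Woman 50 y, 165 cm | 2.570 | 2.612 | 1.016 | 73.8 |
| Man 25 y, 178 cm | 4.292 | 4.379 | 1.020 | 73.5 |
| Man 50 y, 178 cm | 3.617 | 3.704 | 1.024 | 73.2 |
| Girl 12 y, 150 cm | 2.330 | 2.368 | 1.016 | 73.8 |
| Girl 6 y, 115 cm | 0.884 | 0.913 | 1.033 | 72.6 |
| Boy 10 y, 138 cm | 1.928 | 1.988 | 1.031 | 72.7 |
| Boy 7 y, 120 cm | 0.973 | 1.025 | 1.053 | 71.2 |
| Boy 6 y, 115 cm | 0.700 | 0.750 | 1.071 | 70.0 |

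For a 6-year-old boy the ratio runs from 1.056 at 120 cm to 1.101 at 110 cm. Anyone whose true value lies between the last column and 75 is misclassified as normal.

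**Effect on the count in 35 patients.** Simulation, 6000 runs per scenario: sexes equally likely, assumed mean heights by age (SD 5-6.5 cm), true baseline % predicted uniform on 50-110 or 50-100. Mean number wrongly called normal:
- ages 6-30: 0.87 / 1.05
- ages 6-17: 1.10 / 1.32
- ages 18-50: 0.77 / 0.93

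At least one patient is misclassified in 54-74% of trials; the 97.5th percentile is 3-4. The mean level is 1.4-2.0 points too high. A second calculation took true % predicted as normal (mean 70-90, SD 15-20, truncated at 50) and a fixed inflation. It gives 0.5-1.5 patients too few at 1.3-2% inflation and 1.8-3.6 at 5%.

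**Effect on change.** Within a patient the error is a nearly constant multiplier. In the simulation a mean change of 5 shifts by 0.09-0.13 point against a standard error of 9/sqrt(35) = 1.52. The t statistic moves by at most about 0.035, and a correlation with LCI change (set at -0.5) by at most about 0.006.

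**The case against.** The strongest reply is that this is a rounding slip with little reach. The affected output is an exploratory, purely descriptive table. The primary LCI analysis is untouched, and no test or correlation moves by a meaningful amount. In adults the cut-off shifts only from 75 to about 73.2-74.0, while the plan itself assumes an intraindividual FEV1 SD of 9%, so classification near 75% at a single visit is already unstable. The largest ratios come from 6-year-old boys, where the equation predicts under 1 L, and nothing shows how many such patients will enrol. The patient counts rest on assumed heights, ages and baseline values.

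All of that stands as a limit on size. It does not remove the error: measurement noise scatters patients to both sides of the cut-off, whereas this error moves everyone the same way.

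Three limits on scope also stand. First, the documents do not show that the formula feeds the secondary analyses or the screening criterion of at least 50% predicted. Protocol 9.3 has sites enter spirometry data on the CRF, and SAP 2.7.1.5 lists predicted FEV1 among the listed data, so a site-recorded value is possible. Second, the count need not change in a given sample: in 26-46% of the simulated trials nobody fell in the affected band. Third, 2.13.1.6 names a deviation from normal FEV1 in its heading but defines no calculation, so no size can be given for that quantity.

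**Conclusion.** The conversion factor is wrong as written, and nothing elsewhere in the documents corrects it. That every % predicted FEV1 from the 2.13.1.6 formula is too high follows from the equations and needs no assumption about the sample. The size depends on assumed heights: about 1.4-2.4% (relative) in adults aged 25-50, 1.6-3.3% in girls aged 6-12 and 2.6-7.1% in boys aged 6-12. The 75% rule thus becomes an unintended cut-off of about 70-74% that varies with sex, age and height.

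The count of pathological FEV1 can be too low but never too high. An average of about one patient in 35 is a reasonable figure under the assumptions used, with a range from none to a few. The effect on the secondary FEV1 change analyses is negligible even if they use the same formula, which is an inference. The point should be corrected because it biases a stated LCI-versus-FEV1 comparison in one direction and costs almost nothing to put right.

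**What to change.** In SAP 2.13.1.6, replace the conversion with: Height (in inches) = height (in cm)/2.54. Recompute % predicted FEV1, the 75% classification and any deviation from normal FEV1 at baseline and week 4.

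In SAP 2.7.1.1, add a sentence saying that FEV1 % predicted is derived by the formula in 2.13.1.6, or state the other source if one is used.

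The cost is one constant in the derivation program, one cross-reference and a rerun. If the secondary analyses use site-recorded values, only the 2.13.1.6 outputs need rerunning; otherwise all FEV1 % predicted outputs do. Reported values will fall by about 1-3% (relative) in most patients and by more in young boys. No new data are needed.

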2.14 Interim analysis

No interim analysis planned for this study

3 Sample size calculation

The primary effectiveness outcome measure of the study will be the change from baseline to 4 weeks in LCI in patients treated with TBM100. Therefore, sample size calculations for this study are based on the primary objective which produces a precise estimate of these changes in LCI. The precision of the estimated mean change in LCI at 4 weeks, as assessed by the 95% confidence interval

Since LCI is expected to be a more sensitive measure (compared to FEV1), thus the number of patients required to detect changes in FEV1 should also be sufficient to detect relevant changes in LCI and to explore the correlation between LCI and FEV1.

For FEV1, a change of 5% with an intraindividual SD of 9% is expected between on- and off-treatment cycles. Under these assumptions, 28 patients will be required to detect this change with 80% power on a two-sided, 5% significance level. To compensate for some protocol violations and drop-outs, a total of 35 patients should be recruited into this trial.

4 Change to protocol specified analyses

The following changes from protocol have been implemented at the SAP development stage.

Definition of safety set

1. As per protocol: The safety set will consist of all patients that enter the study (provide Informed Consent).
Changes in SAP: The safety set will consist of all patients that enter the study (provide Informed Consent) and have been exposed to at least one dose of study drug.
2. As per protocol: Changes in FEV1 over time-point following onset of study drug inhalation versus Baseline were analyzed.
Changes in SAP: Based on comments on Dry run output from clinical team, changes in FEV1 % predicted instead of changed in FEV1 (L) over time-point following onset of study drug inhalation versus Baseline will be analyzed.

5 Appendix

All statistical output required for drafting CSR were outlined RAP module 7.

5.1 Imputation rules

5.1.1 Study drug

Not Applicable

5.1.2 AE date imputation

AE date imputation is based only on a comparison of the partial AE start date to the treatment start date as mentioned in the Table 1-2 below.

1. If the AE start date year value is missing, the date uncertainty is too high to impute a rational date. Therefore, if the AE year value is missing, the imputed AE start date is set to NULL.
2. If the AE start date year value is less than the treatment start date year value, the AE started before treatment. Therefore:
 - a. If the AE year is less than the treatment year and the AE month is missing, the imputed AE start date is set to the mid-year point (01JulYYYY).
 - b. Else if the AE year is less than the treatment year and the AE month is not missing, the imputed AE start date is set to the mid-month point (15MONYYYY).
3. If the AE start date year value is greater than the treatment start date year value, the AE started after treatment. Therefore:
 - a. If the AE year is greater than the treatment year and the AE month is missing, the imputed AE start date is set to the year start point (01JanYYYY).
 - b. Else if the AE year is greater than the treatment year and the AE month is not missing, the imputed AE start date is set to the month start point (01MONYYYY).
4. If the AE start date year value is equal to the treatment start date year value:
 - a. And the AE month is missing or the AE month is equal to the treatment start month, the imputed AE start date is set to one day after treatment start.
 - b. Else if the AE month is less than the treatment start month, the imputed AE start date is set to the mid-month point (15MONYYYY).
 - c. Else if the AE month is greater than the treatment start month, the imputed AE start date is set to the start month point (01MONYYYY).

Table 1-2: AE date imputation

	MON			
	MISSING	MON < CFM	MON = CFM	MON > CFM
YYYY MISSING	NULL	NULL	NULL	NULL
	Uncertain	Uncertain	Uncertain	Uncertain
YYYY < CFY	(D) = 01JULYYYY	(C)= 15MONYYYY	(C)= 15MONYYYY	(C)= 15MONYYYY
	Before Treatment Start	Before Treatment Start	Before Treatment Start	Before Treatment Start
YYYY = CFY	(B)= TRTSTD+1	(C)= 15MONYYYY	(A)= TRTSTD+1	(A)= 01MONYYYY
	Uncertain	Before Treatment Start	Uncertain	After Treatment Start
YYYY > CFY	(E)= 01JANYYYY	(A)= 01MONYYYY	(A)= 01MONYYYY	(A)= 01MONYYYY

	After Treatment Start	After Treatment Start	After Treatment Start	After Treatment Start
Before Treatment Start		Partial indicates date prior to Treatment Start Date		
After Treatment Start		Partial indicates date after Treatment Start Date		
Uncertain		Partial insufficient to determine relationship to Treatment Start Date		
LEGEND:				
(A)		MAX(01MONYYYY,TRTSTD+1)		
(B)		TRTSTD+1		
(C)		15MONYYYY		
(D)		01JULYYYY		
(E)		01JANYYYY		

Adverse event end date will not be imputed.

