2.8.1 Adverse events (AEs)

The verbatim term recorded on CRF will be identified as adverse event and will be coded by primary system organ class and preferred term using Medical Dictionary for Regulatory Activities (MedDRA) version 18.1 and above, and other version used for coding. Adverse events starting on or after the time of the first inhalation of study drug but not later than 7 days (30 days in the case of a SAE) after the date of last dose of study drug taken or those AE present at baseline with increased severity will be classified as a treatment emergent adverse event and will be included in all summaries. AEs which started and ended prior to baseline and AEs which started prior to baseline but whose severity does not change post baseline will not be included in treatment emergent adverse event.

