Treatment emergent adverse events requiring action to be taken with study treatment will be summarized by primary system organ class and preferred term; overall and by treatment dose form.

Treatment emergent adverse events requiring significant additional medication or therapy

Treatment emergent adverse events requiring significant additional therapy (concomitant medication, non- drug therapy) will be summarized by primary system organ class and preferred term; overall and by treatment dose form.

Treatment emergent adverse events outcome

Treatment emergent adverse events with outcome will be summarized by primary system organ class and preferred term; overall and by treatment dose form.

Treatment emergent serious adverse events

Number and percentage of patients with treatment emergent serious adverse events, regardless of study drug relationship, will be presented by primary system organ class and preferred term; overall and by treatment dose form for safety set.

The patient data listing includes, SOC/PT/Verbatim term, start date/study day, end date/study day, the severity of an AE, whether or not an AE is related to MBW or study drug, and whether or not it is a serious AE, action taken with study drug, outcome, duration. Duration will be calculated as end date – start date+1 and for ongoing last visit date – start date+1.

The following patient data listings will be provided by age group and treatment dose form.

1. Treatment emergent serious adverse event
2. Discontinuation due to treatment emergent adverse events

Additionally, listing of all adverse events and treatment emergent adverse event will be provided for safety set by age group and treatment dose form.

TEAE of special interest

Treatment emergent adverse events of special interest(Elevated BUN and Creatinine, Tinnitus and Hearing loss) will be summarized by primary system organ class and preferred term; overall and by treatment dose form.

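### SAP 5.1.2 can impute an AE start after a recorded pre-treatment end date; precedence over the 2.8.1 exclusion and the class of undated events are unstated, and the duration rule can give zero or negative values

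*SAP*

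**What the plan says.** SAP 5.1.2 sets the scope of the start-date rule: "AE date imputation is based only on a comparison of the partial AE start date to the treatment start date". Three outcomes matter here.

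- Start year equal to the treatment year, month missing or equal to the treatment month (rule 4a): "the imputed AE start date is set to one day after treatment start". Table 1-2 labels these cells as uncertain.
- Start month before the treatment month in the same year (rule 4b): the 15th of that month.
- Start year missing (rule 1): "if the AE year value is missing, the imputed AE start date is set to NULL".

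On end dates the section says only this: "Adverse event end date will not be imputed".

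SAP 2.8.1 defines treatment-emergent events. The inclusion sentence begins "Adverse events starting on or after the time of the first inhalation of study drug but not later than 7 days" after the last dose (30 days for SAEs), and adds events present at baseline that worsened. The exclusion covers "AEs which started and ended prior to baseline and AEs which started prior to baseline but whose severity does not change post baseline". The AE tables in 2.8.1.1 are all tables of treatment-emergent events. A by-patient listing of all AEs is also planned.

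The listing in 2.8.1.1 takes duration as end minus start plus 1 and, "for ongoing last visit date" minus start plus 1. Protocol 6.6.11 and 8.2.2 require SAEs to be reported for 30 days after the last visit.

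**The concern.** A start date with an unknown day or month is ambiguous only while nothing else is known. A recorded end date before first dose settles the matter: the event began before treatment. The rule discards that information and can produce a record whose start is later than its end. A program that derives the treatment-emergent flag from the imputed start will count the event. A program that applies the exclusion first will not. Both follow the SAP.

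The concomitant-medication rule in SAP 5.1.3 shows that a second source can be used: it resolves the same uncertain cells with a flag recorded alongside the date. The AE rule has no such check.

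A null start has the opposite problem. No rule classifies it, and every AE table needs a classification.

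The duration rule is a separate matter. It stops at the last visit although SAEs are collected beyond it, so it can give an impossible value with no imputation at all. At stake are the reproducibility of small safety tables and the credibility of the listings.

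**Working it through.** The plan states no figure on this point, so there is none to reproduce. The check applies the written rules to illustrative dates. Duration = end - start + 1.

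**First dose 20 March 2015, partial start, known end**

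- Start 'March 2015', end 10 March: imputed start 21 March (rule 4a). The first treatment-emergent sentence is met. Duration 10 - 21 + 1 = -10.
- Start '2015', end 25 February: imputed start 21 March, 24 days after the end. The sentence is met. Duration -24 + 1 = -23.
- Start 'March 2015', end 19 March: imputed start 21 March. The sentence is met. Duration 19 - 21 + 1 = -1.
- Start year missing: start null. Treatment-emergent status and duration are both undefined.

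**Rule 4b.** Take first dose 5 April 2015, start 'March 2015', end 12 March. The imputed start is 15 March, correctly before treatment, but duration is 12 - 15 + 1 = -2. Classification is right here; only the listing is wrong.

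These durations assume that the imputed start feeds the duration formula, which the SAP does not state.

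**How often rule 4a misdates such a record.** Take every onset and end pair within the 26 days before treatment (the longest screening period): 26 x 27 / 2 = 351 pairs. Over 365 possible start dates this gives 351 x 365 = 128,115 cases. Assume all are equally likely.

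- Day missing: 42% receive a start after first dose, and 44% a duration of zero or less.
- Day and month missing: 95% and 95%.

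These are shares of events that ended before treatment and have such partial start dates. They are not shares of all AEs.

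**With the start capped at the known end date.** Imputed start = min(SAP start, end date). None of the 128,115 cases keeps a start on or after first dose, and each negative duration above becomes +1. The cap does nothing for null starts or for the next item.

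**Ongoing event starting k days after the last visit.** Duration = last visit - (last visit + k) + 1 = 1 - k. For k = 1 this is 0, for k = 10 it is -9, and for k = 30 it is -29. No imputation is involved.

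**Size of one event.** 1/35 = 2.9%, taking the recruitment target as the Safety Set. The share is larger within a dose form, and the tables are also split that way.

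**The case against.** The strongest reply is that the SAP already excludes these events. In the worked examples the recorded end date proves that the event began and ended before treatment, so the 2.8.1 exclusion applies whatever start is imputed. This stands in part. It defeats any reading that such events necessarily become treatment-emergent. It does not settle the matter, because the SAP never says whether the exclusion is judged on recorded or imputed dates.

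Second, the scenario is rare. Non-serious AEs are scheduled from Visit 2 and only SAEs from consent (Protocol Table 7-1 and 8.2.1). Conditions present before baseline go to medical history (Protocol 7.5.2), and data are queried (Protocol 9.3). Protocol 8.1.1 does define AEs from consent, so the case is possible, but it mainly concerns screening SAEs in patients who are later dosed. This stands as a limit on reach.

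Third, counting uncertain starts as on treatment is a cautious convention. That is fair when the end date is missing or falls on or after first dose. It is no defence when the end date removes the doubt.

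Fourth, a reader might infer that undated events vanish from AE reporting. The documents do not support that. Only a missing year gives a null, an event present at baseline that worsened still qualifies, all AEs are listed, and SAP 2.8.2 lists all deaths.

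Fifth, a reader might infer that negative durations distort the safety tables. They do not: duration appears only in a listing. For a completer, Visit 5 (Day 53 to 56) falls 53 - 28 = 25 to 56 - 28 = 28 days after a last dose on Day 28. An SAE 10 days later is therefore 35 to 38 days after the last dose, outside the 30-day treatment-emergent window. Protocol 8.4 also words the SAE period differently, running it only to the last visit, but 6.6.11 and 8.2.2 both extend it by 30 days.

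**Conclusion.** The point holds as a minor one. Two written rules give wrong outputs: rule 4a can date an event after its own recorded end, and the duration rule gives 0 to -29 days for an ongoing SAE starting 1 to 30 days after the last visit. Two further matters are gaps rather than errors: which of the 2.8.1 sentences prevails, and how a null start is classed. Miscounting as treatment-emergent, and omission from the AE tables, are therefore possible and not certain.

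The documents give no basis for an event count. With about 35 patients, at most 26 days of screening and mainly SAEs collected before Visit 2, very few events should be affected, possibly none. One event would move a table entry by 2.9 percentage points if the Safety Set is 35. The primary LCI analysis is not affected.

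**What to change.** In SAP 5.1.2, add three statements:

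1. If the AE end date is known, the imputed start may not be later than it.
2. An event whose end date is before first dose is not treatment-emergent, whatever start is imputed.
3. An event with a null start is treatment-emergent unless its end date is before first dose.

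In SAP 2.8.1.1, run the duration of ongoing events to the date of last contact, or leave it blank when onset is after the last visit.

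The cost is a few sentences and a small programming change. There are two small drawbacks. The third statement may over-count an undated event that in fact preceded treatment. A start capped at the end date shows a one-day duration that comes from the imputation, so imputed dates should be marked in the listing.
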